
## MEDICAL PROTOCOL (HRP-590)

PROTOCOL TITLE: Magnesium sulfate as adjuvant analgesia and its effect on opiate use by post-operative transplant patients in the pediatric ICU.

VERSION DATE: 06/09/2022

be restarted. Should the infusion be discontinued, once magnesium levels normalize we will plan to check magnesium levels at discretion of primary team rather than study intervals, so as to minimize risk of anemia and excessive accessing of central line. If levels are not able to be drawn due to some other unpredicted variable (patient participating in physical therapy, patient escorted down to gift shop, patient had emergent surgical intervention for other reasons, etc), blood draw will be performed at earliest availability. This is standard of care for any serial blood draw ordered on the unit. If there is an adverse event that there is concern magnesium may be contributing, the infusion will be immediately turned off until further investigation deems safe to restart. Any adverse event deemed secondary to magnesium will result in indefinite discontinuation of the infusion, notification of safety monitor, and review of study protocol as outlined elsewhere. This is discussed further in risk sections. Despite magnesium being an approved elemental agent, based on the above protocol and the extended duration of magnesium infusion compared to available literature, as well as the absence of previous research in our targeted population, this proposed project was submitted to and approved by the FDA under an IND application. Based on the sources discussed above in existing literature section, our dosing protocol has been tried intraoperatively in both pediatrics and adults without side effect and demonstrated levels below which cause hemodynamically relevant side effects. Further data (asthma in pediatrics, multiple purposes in adults) have demonstrated prolonged durations of magnesium infusion at comparable doses without adverse effects, including durations longer than our proposed 48 hours. Additionally, some studies mentioned reached higher levels than our proposed target and remained free of side effect.

- 4.2. Drug/Device Handling: This is an IND research study, in which case the Investigational Drug Service at UMN will monitor handling of magnesium including ordering, storage, and handling of the medication. OnCore programming will be used for IDS-monitoring and study's protocol schedule. Costs for medication and drug levels will be paid for by grant funding. Nurses perform 2-person checks to confirm all ICU-delivered medications, which will include MgSO4. This includes checking name of medication, dose, and infusion rate when starting the medication. There will be no change-over to a new MgSO4 bag at transfer from OR to PICU. The medication is already currently ordered and stored at the UMN, so would not otherwise require any new/additional hospital design, other than pharmacy and IDS tracking any shortage of supply.
- 4.3. Biosafety: n/a
- 4.4. Stem Cells: n/a
- 4.5. Fetal Tissue: n/a

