## 12. Withdrawal of Participants

**12.1. Withdrawal Circumstances:** Participants are free to withdraw from participation in the study at any time upon request. An investigator may terminate participation in the study if:

1. Any clinical adverse event (AE), such as secondary toxic reaction to magnesium sulfate, laboratory abnormality, or other medical condition or situation occurs such that continued participation in the study would not be in the best interest of the participant. Specifics regarding secondary reactions:
  - regarding the hemodynamic adverse effects of magnesium: the drug will be halted for etiologic evaluation in the presence of confirmed hypotension or sustained bradycardia; if deemed secondary to magnesium that patient's therapy will be permanently discontinued
  - regarding sedative effects: the PICU team addresses sedation goals each day with rounds and follow up; preference with over-sedation will be to decrease other analgesia/sedative infusions as able given overall goal of this study (i.e. lower opioids, benzodiazepines, dexmedetomidine first as able). If deemed unable to decrease other infusions or already at a minimum, and over-sedation still present, then magnesium infusion will be discontinued.
  - regarding frequency of blood draws: blood draws are already frequent in this population of patients in initial 2 days post-op (typically every 6

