*12.3. Termination Procedures:* This study may be temporarily suspended or prematurely terminated if there is sufficient reasonable cause. Written notification, documenting the reason for study suspension or termination, will be provided by the suspending or terminating party to investigator, funding agency, the IND sponsor and regulatory authorities. If the study is prematurely terminated or suspended, the PI will promptly inform the IRB and will provide the reason(s) for the termination or suspension. The study team will notify the participants of the study termination. Specifically, the study will be halted if 2 patients develop clinically significant adverse reactions secondary to magnesium, at minimum until able to further review dosing and protocols. If arrhythmia (other than transient bradycardia), respiratory failure, or coma encountered once (also deemed secondary to magnesium), the study will be halted immediately with that patient until able to review with IRB and FDA. Per above, if encountering more frequent anemia than typical post-transplant course on multiple patients, the study will be halted to evaluate lab frequency's effect. The study will also be halted for further review if there is a dosing error.

Circumstances that may warrant termination or suspension include, but are not limited to:

- Determination of unexpected, significant, or unacceptable risk to participants
- Demonstration of efficacy that would warrant stopping
- Insufficient compliance to protocol requirements
- Data that are not sufficiently complete and/or evaluable

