## 13. Risks to Participants

*13.1. Foreseeable Risks:* This would include the potential for known side effects from magnesium toxicity, namely: hypotension, cardiac arrhythmia, hyporeflexia, effects on other electrolytes (such as potassium and calcium), muscle weakness, respiratory depression (secondary to muscle weakness), and increased sedation (including when combined with opioids and benzodiazepines). These toxic risks are cited typically at levels of > 4-4.5 mg/dL. We will minimize this risk by targeting magnesium thresholds below this. Hypotension is monitored for via routine serial blood pressure monitoring in all ICU patients, and can be treated with IV fluid resuscitation as needed (standard for hypermagnesemia treatment). Cardiac arrhythmia is monitored for via cardiac telemetry in all ICU patients, and cardiology specialists and arrhythmia resuscitation techniques are available per standard ICU care. Both of these are risk factors that are present in these populations regardless of magnesium use, however if these conditions are felt potentially contributed to by hypermagnesemia the infusion will be stopped for further evaluation. Electrolyte abnormalities are also common in ICU populations and are monitored routinely per post-transplant protocols. Respiratory depression is monitored routinely in this population as well, however if secondary to perceived muscle weakness out of proportion to standard post-operative course, the magnesium infusion will be stopped as well. Sedation and other analgesia is routine in post-operative transplant care and is addressed and titrated based on daily goals. Decreasing other sedatives will take precedent over magnesium in cases of oversedation given the overall objective of the study. Increased blood draws may occur during monitoring, however in 48 hours of infusion may result in only 4-8 mL of extra blood specifically from magnesium draws alone, which clinically seems insignificant relative to overall course. There is potential for dosing error as is for all PICU delivered medications, however correct units for MgSO4 has been updated in UMMCH pump library, and there is additionally standard ICU regulations per institutional and leadership for routine drip/dose checks. The only other potential foreseeable risk would be that of intravenous line capability. Post-operative transplant patients require multiple IV

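### For over-sedation during the infusion, section 4.1 turns magnesium off at once on suspicion, while sections 12.1 and 13.1 lower other drugs first and stop magnesium last

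*Combined protocol and SAP*

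**What the plan says.** Section 4.1 (Description) has two steps. On suspicion: "If there is an adverse event that there is concern magnesium may be contributing, the infusion will be immediately turned off", until an investigation finds it safe to restart. On attribution: "Any adverse event deemed secondary to magnesium will result in indefinite discontinuation of the infusion", with notice to the safety monitor and a review of the protocol. It then adds: "This is discussed further in risk sections".

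Section 12.1 (Withdrawal Circumstances) deals with sedation in its own bullet. The first step is that "preference with over-sedation will be to decrease other analgesia/sedative infusions as able given overall goal of this study"; opioids, benzodiazepines and dexmedetomidine are the drugs named. The last step is: "If deemed unable to decrease other infusions or already at a minimum, and over-sedation still present, then magnesium infusion will be discontinued".

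Section 13.1 (Foreseeable Risks) names "increased sedation (including when combined with opioids and benzodiazepines" among the known effects of magnesium toxicity. Later in the same section it says: "Decreasing other sedatives will take precedent over magnesium in cases of oversedation given the overall objective of the study".

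Sections 3.1 and 12.3 carry the study-level rule that "the study will be halted if 2 patients develop clinically significant adverse reactions secondary to magnesium".

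**The concern.** An over-sedated child on magnesium plus an opioid or other sedative infusion is a foreseeable case in this population, and the protocol recognises magnesium as a possible contributor. Under one section the pump goes off at once. Under the other two it keeps running while other drugs are weaned. Staff need one instruction for a named toxicity in children.

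Three things depend on which text is followed:

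- **Magnesium exposure** in the treated group.
- **The count of holds.** Section 15.1 collects how often the infusion was held over adverse event concern. An over-sedation episode adds to that count under 4.1 but need not under 12.1.
- **Possibly the primary outcome.** This is total opioid dose per kg, compared with retrospective controls. The 12.1/13.1 route reduces opioids in an over-sedated treated child by study instruction and cites the study's goal as the reason. The controls were not under that instruction. Part of any observed difference could then reflect the rule and not a reduced need for opioids.

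**Working it through.** No figure in the plan bears on this point, so the check is a comparison of texts.

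**Step 1. Does over-sedation fall under 4.1?** The 4.1 rule needs an adverse event and a concern that magnesium may contribute.
- Section 18.2 defines an adverse event broadly, as any symptom or sign that appears or worsens during the study, related or not. Over-sedation can meet that definition.
- Section 13.1 lists increased sedation as a magnesium toxicity effect, and section 18.2 says the study product is always to be suspected. The second condition can therefore also be met.

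**Step 2. Apply each rule to one case:** an over-sedated child on magnesium and an opioid infusion that can still be lowered, with magnesium suspected.

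| Section | Magnesium now | Other infusions | When magnesium stops |
|---|---|---|---|
| 4.1 | Off immediately | Not addressed | At once; permanently if attributed |
| 12.1 | Continues | Lowered first, as able | Only if the others cannot be lowered or are at a minimum, and over-sedation persists |
| 13.1 | Continues | Lowered before magnesium | Not stated for over-sedation |

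Doing both, by stopping magnesium and lowering the other drugs together, satisfies 4.1 but not 12.1 or 13.1, which put magnesium after the other drugs. No single action satisfies all three.

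**Step 3. Is the conflict wider than over-sedation?** No. For confirmed hypotension or sustained bradycardia, 12.1 halts the drug for evaluation. For hypotension or arrhythmia to which high magnesium may contribute, and for respiratory depression from disproportionate muscle weakness, 13.1 stops the infusion. All of these broadly agree with 4.1.

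**Step 4. Is an exception written anywhere?** Section 4.1 points to the risk sections for further discussion but does not make its rule subject to them. Section 12.1 introduces its bullets as specifics for secondary reactions but does not say that the sedation bullet displaces 4.1. Section 13.1 does not mention 4.1.

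**Step 5. Is over-sedation visible in the safety review?** The section 18.2 safety list covers hypotension, respiratory decline, arrhythmia and electrolytes. Sedation appears only as something to relate to respiratory decline. The safety monitor also receives other unforeseen events possibly due to magnesium, but over-sedation is foreseen in 13.1.

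**Step 6. Can the effect be sized?** No. The documents give neither a rate of over-sedation nor the opioid reduction that would follow an episode. Any number would be invented.

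**The case against.** The best defence is that 4.1 is the general rule and 12.1 the specific one. Section 4.1 refers onward to the risk sections, 13.1 is such a section, and 12.1 separates haemodynamic, sedative and blood-draw reactions. That is a fair way to read the intent. It does not remove the contradiction, because 4.1 is worded without exception and the protocol never says which text prevails.

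Second, 12.1 states a preference, qualified by feasibility, and ends in discontinuation. This stands as a limit: the sections disagree on order and timing, not on whether magnesium is ever stopped. A reader who infers that 12.1 and 13.1 keep magnesium running regardless goes too far.

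Third, section 18.1 tells staff to page the study team about side effects, restricts who may change magnesium orders, and keeps a study member reachable at all times. This narrows the practical risk of divergent bedside decisions. But the study team works from the same conflicting text, and 18.1 defers to the medical team when the investigators are not present.

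Two stronger readings are tempting and are not supported:

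- A reader might infer that the 12.1 route bypasses causality assessment, so that events escape the two-patient halt. Section 18.2 requires every adverse event to be recorded and its relationship to the intervention assessed, whichever drug is lowered first. Nor does 4.1 attribute every event: suspicion and attribution are separate steps there. The two sections therefore do not imply two different probabilities of a halt.
- A reader might infer that the reported over-sedation rate cannot be interpreted. No such rate is a listed outcome in section 15.1; sedation could appear only under the type of magnesium-related adverse event.

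**Conclusion.** Wrong as written: an internal contradiction, confined to over-sedation. It rests on two conditions, that the episode meets the adverse event definition and that magnesium is suspected. The protocol's own wording makes both readily met. If either fails, 4.1 is not triggered and there is no conflict for that child.

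The effects on exposure and on the count of holds follow directly from the rules. The effect on the primary outcome is possible, not shown. Opioids may also have been reduced in over-sedated controls under usual care, which the documents do not describe.

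This is more than missing detail, because the stated rules give different actions for the same child. It should be resolved, since it concerns a named toxicity and is cheap to correct. No view is taken here on which clinical rule is right.

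**What to change.** 1. Reconcile sections 4.1, 12.1 and 13.1 so that one rule, chosen by the sponsor and the safety monitor, governs over-sedation during the infusion. The other sections should refer to it.
2. State that managing over-sedation by lowering other drugs does not remove the duty already in section 18.2. An episode that meets the adverse event definition is recorded and assessed for causality. If it is deemed secondary to magnesium and clinically significant, it counts toward the halt rule in 12.3.
3. Add over-sedation as its own item in the section 18.2 safety list, so that it reaches the safety monitor's scheduled reviews without depending on respiratory decline.

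The cost is a protocol wording amendment, one added item in safety data capture, and notice to staff. No new data source is needed.

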## MEDICAL PROTOCOL (HRP-590)

PROTOCOL TITLE: Magnesium sulfate as adjuvant analgesia and its effect on opiate use by post-operative transplant patients in the pediatric ICU.

VERSION DATE: 06/09/2022

### 5. Procedures Involved

#### 5.1. Study Design:

Experimental Group: Prospective Cohort of next 30 incoming liver and TPIAT transplant children which meet inclusion criteria. Due to the more difficult predictability of when liver transplants occur, and to ensure adequate enrollment of 30 patients occurs within the 3-year pilot duration, we have chosen not to have a 50/50 balanced prospective cohort.

Control Group: Control will be via retrospective chart review of the last 60 transplant patients from the same population (liver, TPIAT) with same surgeon. Intervention and data collection will be as outlined elsewhere in protocol.

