## MEDICAL PROTOCOL (HRP-590)

PROTOCOL TITLE: Magnesium sulfate as adjuvant analgesia and its effect on opiate use by post-operative transplant patients in the pediatric ICU.

VERSION DATE: 06/09/2022

Control Group: For collection of control data, a MRN list of the most recent 60 transplant patients under the same surgeon at this institution (30 liver, 30 TPIAT) who have not opted out of research will be obtained via UMN's Best Practices Integrated Informatics Core (BPIC), followed by access to EPIC EMR outside of the Information Exchange to review patient's chart and collect for intended outcomes, which are also uploaded into RedCap. This will be done in identical manner as that for prospective data collection — the EMR will be accessed for appropriate patient by MRN, followed by selecting the appropriate surgical encounter by date, followed by selecting only specific portals in epic where intended data elements are located (for example: Intake/Output section, or results review -> magnesium level, etc). Collection of this data will be initiated at the start of IRB approval and ongoing to completion. Full data analysis will be completed at conclusion of study followed by construction of manuscript. Of note, hypomagnesemia is corrected per standard ICU care with IV MgSO4 regardless of study, and liver transplant patients currently have a pre-designed magnesium replacement protocol (also used in our CVICU post-operative cardiac patients). This will still be included in data collection without adjustment to any comparison data in statistical analysis. This replacement protocol will not be used in our study as we will already be providing continuous IV MgSO4. Similarly, magnesium blood levels are checked independent of this study, although will be more frequent now for safety monitoring. These blood levels are drawn through a central line that is already in place independent of this study, so will not require percutaneous needle stick. There are no other drugs/devices involved in study or that would alter MgSO4 delivery.

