### Experimental Group:

1. Male or female of at least 3 years and <18 years of age at screening.
2. Written informed consent from participant's legal representative and assent (when applicable) obtained from participant and ability for participant to comply with the requirements of the study.
3. Stated willingness to comply with all study procedures and availability for the duration of the study
4. Be scheduled for and receive a liver transplant or total pancreatectomy and islet cell autotransplantation

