### Control Group:

1. Male or female of at least 3 years and <18 years of age at transplantation.
2. Received a liver transplant or total pancreatectomy and islet cell autotransplantation.

8.2. Exclusion Criteria: An individual who meets any of the following criteria will be excluded from participation in this study:

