## MEDICAL PROTOCOL (HRP-590)

PROTOCOL TITLE: Magnesium sulfate as adjuvant analgesia and its effect on opiate use by post-operative transplant patients in the pediatric ICU.

VERSION DATE: 06/09/2022

access to their medical records. Potential participants will be asked about their interest in the study at the time of the pre-transplant visit.

All potential participants will be those that have become eligible for transplantation with our pediatric transplant surgeons. No other recruitment strategies will be used. The transplant surgeon (also a co-investigator of this study) will make initial contact with these patients/families, and will describe the intended treatment plan including consent for our study. The surgeon and PI will be in contact regarding each upcoming transplant patient that will be cared for in the PICU, in addition to consent and HIPAA authorization forms being added to patient chart so that can be confirmed at admission to the PICU.

Control Group: The records used in the study for the control group are the records of the patients in the investigators' clinical practices. Any medical records marked with the opt-out-research flag will not be viewed. A list of the past 60 patients based on inclusion criteria will be obtained from the BPIC at the UMN.

*11.3. Recruitment Materials: n/a*

*11.4. Payment: n/a*

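### Controls are limited to one surgeon's patients but the magnesium group is not, so surgeon practice may be partly confounded with magnesium if a second surgeon operates on any prospective patient

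*Combined protocol and SAP*

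**What the plan says.** **Controls.** Section 5.1 states: "Control will be via retrospective chart review of the last 60 transplant patients from the same population (liver, TPIAT) with same surgeon". Section 5.2 describes the list to be requested from the informatics core as the "most recent 60 transplant patients under the same surgeon at this institution", split into 30 liver and 30 TPIAT. The control inclusion criterion on surgery in section 8.1 names only the procedure ("Received a liver transplant or total pancreatectomy and islet cell autotransplantation"), and section 11.2 describes the source as the practices of the investigators, in the plural.

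**Magnesium group.** Section 5.1 describes a "Prospective Cohort of next 30 incoming liver and TPIAT transplant children which meet inclusion criteria". The inclusion criterion on surgery in section 8.1 is "Be scheduled for and receive a liver transplant or total pancreatectomy and islet cell autotransplantation". No surgeon condition appears in sections 8.1 or 8.2, and section 8.3 treats any transplant patient who is not pregnant as eligible. Section 11.2 says "All potential participants will be those that have become eligible for transplantation with our pediatric transplant surgeons", and also allows identification among patients of the investigator's colleagues.

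**Text pointing to one surgeon.** Section 11.2 continues: "The transplant surgeon (also a co-investigator of this study) will make initial contact with these patients/families". Section 8.3 has the co-investigator surgeon take the procedural consent at the same time as the study consent. Section 11.1 has that surgeon introduce the study to all liver patients. Section 19.2 places all patients within that surgeon's and the PI's practice area.

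**Analysis.** Operating surgeon is not in the section 15.1 data list. The adjusted primary model in section 15.3 has covariates for study group, transplant type, age and gender.

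**The concern.** The comparison is with historical controls, so its validity depends on the two groups differing in little besides magnesium. The plan treats the surgeon as worth holding constant, but writes the restriction for the controls only. As the eligibility rules stand, a child operated on by another surgeon could receive magnesium, while that surgeon's earlier patients could not be controls. Any difference between surgeons in operative technique or perioperative analgesic habit would then enter the estimated magnesium effect. It could imitate an opioid-sparing effect or hide one. The planned covariates would not address it, and without the surgeon in the dataset a reader could not see whether it had happened.

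**Working it through.** **Step 1: the surgeon rule, place by place.**

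| Place | Controls | Magnesium group |
|---|---|---|
| 5.1 | same surgeon | next 30 meeting inclusion criteria |
| 5.2 | same surgeon | no surgeon stated |
| 8.1, 8.2 | no surgeon condition | no surgeon condition |
| 8.3 | not addressed | any non-pregnant transplant patient; one surgeon takes consent |
| 11.1 | not addressed | one surgeon introduces the study to liver patients; pain team introduces it to TPIAT patients |
| 11.2 | investigators' practices | surgeons (plural), colleagues' patients; one surgeon makes first contact |
| 19.2 | one surgeon's and the PI's practice area | the same |

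The written eligibility rules permit a one-sided restriction. The recruitment text suggests it may not arise in practice. No sentence settles who operates on the prospective patients.

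**Step 2: the plan's own figure.** Section 15.2 gives SD 8.3 mg/kg and mean 15.5 mg/kg for the 7-day total, and 3.49 mg/kg (20%) as detectable with 80% power at 90 per group. A two-sample t-test calculation, two-sided 5%, gives 3.49 mg/kg (normal approximation: 8.3 × √(2/90) × 2.802 = 3.47). The 20% follows if 15.5 is the mean over both groups: 3.49 / (15.5 + 3.49/2) = 20.2%. The figure reproduces.

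**Step 3: precision at the planned 60 controls and 30 prospective patients.** SE = 8.3 × √(1/60 + 1/30) = 1.856 mg/kg.

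**Step 4: possible bias.** Let f be the share of prospective patients operated on by another surgeon, and s the difference in opioid use between surgeons as a share of the mean. Then bias = f × s × 15.5. The documents give neither f nor s; both are assumptions. The chance of a significant result when magnesium has no effect is Φ(bias/SE − 1.96) + Φ(−bias/SE − 1.96).

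| f (assumed) | s (assumed) | Bias, mg/kg | Share of 3.49 | False-positive rate |
|---|---|---|---|---|
| 0 | any | 0 | 0% | 5.0% |
| 0.10 | 10% | 0.16 | 4% | 5.1% |
| 0.25 | 20% | 0.78 | 22% | 7.0% |
| 0.50 | 20% | 1.55 | 44% | 13.3% |
| 0.50 | 30% | 2.32 | 67% | 24% |

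Example, third row: 0.25 × 0.20 × 15.5 = 0.775.

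**Step 5: the price of restricting the analysis to the control surgeon.** With all 60 controls kept, the minimum detectable difference at 80% power is 8.3 × √(1/60 + 1/n) × 2.802.

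| Prospective patients removed | n left | Detectable difference, mg/kg | Power for 3.49 mg/kg |
|---|---|---|---|
| none | 30 | 5.20 | 47% |
| 10% | 27 | 5.39 | 44% |
| 25% | 22 | 5.80 | 39% |
| 50% | 15 | 6.71 | 31% |

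**The case against.** The best reply is that the phrase in section 5.1 is relational. It directly follows the description of the magnesium group, so it can mean the same surgeon as that group's, which would make the surgeon common to both by intent. Sections 8.3, 11.1, 11.2 and 19.2 all name one co-investigator surgeon, and section 8.3 has that surgeon take consent for the operation itself. On that reading f = 0 and there is no bias. Much analgesic management also lies with the pain team and the PICU rather than the surgeon, so s may be small.

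Most of this stands as a reason for caution. It does not close the gap. Taking consent or making first contact does not fix who operates. TPIAT families may be approached and consented through the pain team (sections 11.1 and 21.1). The practice-area sentence in section 19.2 concerns chart access and also names the PI.

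Two stronger inferences are tempting and are not supported. One is that the design section and the eligibility section define incompatible control populations: a sampling list and patient-level criteria can apply together, although section 8.1 should carry the surgeon rule. The other is that a surgeon effect could never be removed later. The operating surgeon is in the medical record, the surgical encounter is opened for each patient (section 5.2), and record numbers are held in REDCap (section 16.9), so it can be retrieved until the identification key is destroyed at completion (section 15.4).

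**Conclusion.** The documents restrict controls by surgeon and do not state a matching restriction for the magnesium group. Confounding of surgeon with magnesium is therefore possible. A reader might infer that it is established, or that patients of every transplant surgeon will be enrolled. The plural in section 11.2 and the silence of section 8.1 do not show that, given the text pointing to one surgeon.

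Any confounding would also be partial, since prospective patients of the control surgeon remain comparable with the controls in this respect. Its size runs from nil, if one surgeon performs all 30 operations, to material: 1.55 mg/kg, or 44% of the planning difference, if half the group had another surgeon and surgeons differed by 20%. These figures rest on assumed inputs and on an SD and mean from a 7-day total in a pediatric TPIAT study, whereas the primary analysis uses the whole PICU stay. They illustrate scale and are not estimates. The point merits correction because the remedy is cheap and the comparison is not randomised.

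**What to change.** 1. State one surgeon rule in section 8.1 that applies to both groups, and bring sections 5.1, 5.2 and 11.2 into line with it. If one surgeon performs every operation, saying so is enough for this step.
2. Add operating surgeon to the section 15.1 data list for both groups, and report the surgeon mix by group.
3. If more than one surgeon contributes prospective patients, pre-specify in section 15.3 a sensitivity analysis of the primary comparison restricted to patients of the control surgeon or, if controls are drawn from several surgeons, adjusted for surgeon.

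Two cautions apply. A surgeon covariate does not help while all controls come from one surgeon, because other surgeons' patients then carry no information on the magnesium effect. Widening the controls to any surgeon with a prospective case does not by itself balance the surgeon mix, so steps 2 and 3 would still be needed.

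The cost is one eligibility line, one field already in the medical record and one conditional analysis. Limiting the magnesium group to one surgeon could slow enrolment; widening the controls means a new record query. The restricted analysis loses precision: with 25% of prospective patients excluded, the minimum detectable difference rises from about 5.2 to 5.8 mg/kg.
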